Aim 1: We will randomize **304 participants**; 76 to CM alone, 76 to CM+NH, 76 to CM+ ER, and 76 to CM+NH+ER. Based on the previous work with the SIQ, we believe a 25% reduction among individuals with a score of 30 or greater would represent clinically significant change in suicide ideation.[5] Using pilot data of NH among the WMAT, an average baseline score of 45 could be expected on the SIQ.[5] A clinically significant reduction translates into a large Cohen's D effect size (>0.8). However, we want the power to observe the more moderate effect expected to result from comparing the sequencing of the interventions (NH+ER vs. NH+CM vs. CM+ER vs. CM alone). Using an adjusted alpha to account for multiple comparisons of 0.013, and a correlation of 0.2 among repeated measures, with four groups (NH+ER vs. NH+CM vs. CM+ER vs. CM alone), $n=58$ people per group ($n=116$ randomized at each randomization time-point) would provide 80% power to detect a small to moderate effect (Cohen's $F=0.2$). Adjusting these estimates for 30% attrition would result in $n=76$ per each of the four groups ($n=152$ per arm) for a total sample size of $N=304$.

Please note for our ***the Opioid Data Collection Sub-Study***: We will use a mixed methods approach to examine opioid use among our SMART trial participants through addition of a quantitative opioid related measure and qualitative interviews ($N=30$) with a subset of those who endorse recent or current use.

For the economic evaluation supplement: We will use the same sample of participants as Aim 1. We are not drawing statistical inferences about cost estimates so there is no sample size requirement. Instead, we are reporting on the health care services utilization and costs incurred by study participants before, during and after the intervention. To administer a time use survey and conduct in-person interviews we will use all HUB program case managers (five or more) and healthcare providers (three or more).

For the diversity supplement: We will use a sub-sample of $n=239$ WMAT participants enrolled in the parent trial. This sample size is based on the estimated enrollment rates during the Diversity Supplement study period.

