Randomization Procedure 1. Participants will be stratified by age groups (10-14, 15-19, and 20-29) and event type (ideation, attempt, binge + recent ideation), then randomized to the control or intervention condition using a 1:1 assignment ratio. Re-randomization of all participants will occur again at **CM3** (another 30 days or 60 days/2 months post-baseline assessment).

Control Condition: Monitoring and Case Management (CM): Research Program Assistants, who are trained Surveillance System Staff, will conduct the monitoring and case management visits in participants' homes or other private settings at baseline, 1, 2, 3 and 6 months post-enrollment. This time-period was selected as the highest risk period for a subsequent suicide event following an initial episode.[12, 13] The CM visit includes rapport-building, use of the Suicide Ideation Questionnaire (SIQ) to assess imminent risk, and if youth report not yet having connected to services, referral to Apache Behavioral Health Services (ABHS), the local community mental health center. As we have added opioid related questions through an administrative supplement, the monitoring and case management visits will also allow us to track any safety concerns related to opioids and provide appropriate referrals to treatment. If minors seek treatment elsewhere or express disinterest, case managers will also facilitate connections to other care providers

(traditional healers, church, IHS social services/mental health, and private providers). At CM visits, the **Research Program Assistants will also monitor participants' completion of the study battery**, which will be self-administered using tablets. In addition, Research Program Assistants will score the SIQ before leaving the youth. If the SIQ reveals the participant is at imminent risk, Research Program Assistants will employ a protocol for rescue services (*described below*), which involves triaging youth immediately to the ED for further assessment and care.

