Aim 3: The qualitative interview should take no longer than 45 minutes and will be done at a convenient time. There will only be one-two study visits, although stakeholders will be encouraged to provide feedback at any time about their experiences with the Southwest Hub's key intervention components. For the online survey, the survey is expected to take 20 minutes and will be administered twice a year in years 2-5, for a total of 8 time points. *The opioid roundtables are estimated to take 60-90 minutes.*

4. Provide a brief data analysis plan and a description of variables to be derived.

Primary and Secondary Outcomes

Aim 1: Given the longitudinal nature of the data, we will use mixed-effects regression models (MRMs)[41] to estimate average treatment effects while accounting for shared variance of repeated measures within adolescent. MRMs are highly flexible, addressing: variability in number and spacing of measurements, a variety of outcome distributions, linear and non-linear patterns of change (e.g., quadratic), and are robust to missing data.

Suicide ideation (primary outcome): Measured by the Suicide Ideation Questionnaire (SIQ/SIQ-JR). The SIQ is a 15-item scale that analyzes frequency and severity of suicidal ideation over the past 6 months. Items are scored on a 7-point scale ranging from 0 “I never had this thought” to 6 “Almost every day.” Scores of 30 for the SIQ and 23 for the SIQ-JR indicate severe suicidal ideation and need for clinical intervention. The scale has been used among AI adolescents with sound psychometric properties (Cronbach’s alpha=0.97).[22]

Resilience (secondary outcome): Measured by The Resiliency Scales. These are self-report scales measuring the individual’s Sense of Mastery (MAS; composed of 20 items), the Sense of Relatedness (REL; 24 items), and the Emotional Reactivity (REA; 20 items). Each item has five response choices ranging from 0 (Never) to 4 (Almost Always).

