Aim 1: The PIs assume responsibility for the safety of study participants. Research Program staff will be trained to monitor for safety of study participants and report any concerns immediately to the Local Project Director, the Clinical Research Supervisor and the PIs. All Research Program staff will be trained in human subject's research and will be required to complete the CITI ethics module prior to any interaction with participants or study data. Certificates of human subject's completion will be kept on file at the Center for American Indian Health's office in Baltimore.

To determine and quantify the participant's current risk for suicide at the close of all study visits, the Research Program Assistants will complete the Suicide Ideation Questionnaire (SIQ) (participants 15 and over) or the SIQ-JR (participants <15years) with participants. The screen will identify recent suicidal ideation

or behavior, worsening of psychopathology and recent acute stressors. Research Program Assistants will immediately score the SIQ. Depending on the SIQ score, the Research Program Assistants will administer the SIQ-Past Few Days, and then respond in a graduated fashion based on the following risk categories as determined by the SIQ /SIQ-Past Few Days: 1) Does not Appear at Risk; 2) At Some Risk; 3) At Medium to Very High Risk. The following actions, which are clearly outlined in the consent form and will be reviewed prior to each assessment, are taken depending on the SIQ/SIQ-Past Few Days Risk Score:

If the SIQ score is below 37 or SIQ-JR is below 16, the risk category is deemed to be **“Does Not Appear at Risk.”** Research Program Assistant takes the following steps:

When the SIQ does not identify any acute risks and Research Program Assistant observations corroborate this impression, no additional immediate action is needed. If staff has any concerns about these participants, they should not hesitate to contact:

- Local Project Director, [name], Whiteriver, AZ
- Principal Investigators, [name], PhD and [name], PhD, Baltimore, MD
- Clinical Research Supervisor, [name] [name], PhD, Baltimore, MD

If the SIQ score is 37 or above, the SIQ-Jr is 16 or above, and 0 items on the SIQ-Past Few Days scored a 4, 5, or 6 the risk category is deemed to be **“At some risk”**.

Research Program Assistants take the following steps:

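### SIQ scores of 30–36 at age 15 and over count as severe in the outcome definition but as the lowest risk category in the safety rule, and nothing reconciles the two

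*Combined protocol and SAP*

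**What the plan says.** Four places in the combined protocol and SAP bear on how an SIQ total is read.

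- **V.C.4, Suicide ideation (primary outcome).** "Scores of 30 for the SIQ and 23 for the SIQ-JR indicate severe suicidal ideation and need for clinical intervention". The look-back is given there too: "The SIQ is a 15-item scale that analyzes frequency and severity of suicidal ideation over the past 6 months".
- **III.B, sample size for Aim 1.** The same mark, with its direction: "we believe a 25% reduction among individuals with a score of 30 or greater would represent clinically significant change in suicide ideation".
- **X.C.1, Safety Monitoring.** Staff use the SIQ at age 15 and over, or the SIQ-JR below 15, to judge "current risk for suicide at the close of all study visits". The rule begins "If the SIQ score is below 37 or SIQ-JR is below 16, the risk category is deemed to be" the lowest category, whose label says the participant does not seem to be at risk. The instruction for that category is: "When the SIQ does not identify any acute risks and Research Program Assistant observations corroborate this impression, no additional immediate action is needed". The two higher categories start at SIQ 37 or SIQ-JR 16. They are separated by the SIQ-Past Few Days items, and both require a call to the Local Project Director.
- **VII.C.e, Dangerousness to self.** The SIQ-Past Few Days is given, and a safety plan made, when the score is above the developers' clinical cutoff. No number is stated.

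The Control Condition text in V.C.1 also describes "use of the Suicide Ideation Questionnaire (SIQ) to assess imminent risk" as part of each case management visit.

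**The concern.** One score on one instrument has two meanings. A participant aged 15 or over who scores between 30 and 36 is, by the outcome definition, severely ideating and in need of clinical intervention. By the safety rule the same participant is in the category that needs no further immediate step, provided staff observations agree.

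Participants are enrolled because of a recent attempt, recent ideation, or binge substance use with recent ideation, and staff score the form and act on it before leaving. If the figure in V.C.4 is the right one, the safety rule starts too late for this band. If 37 is right, V.C.4 misdescribes the instrument or needs an explanation. Either way, staff who turn to VII.C.e find a trigger without a number.

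The statistical inference is not at stake. A score of 30 is not an eligibility criterion, and no stated analysis splits the SIQ at 30 or 37.

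**Working it through.** No power, alpha or sample-size figure is in question. The check applies each written rule to each possible score.

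**Inputs**

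- Severity mark: SIQ 30, SIQ-JR 23 (V.C.4). Direction for the SIQ: 30 or greater (III.B).
- Safety rule: lowest category if SIQ < 37 or SIQ-JR < 16 (X.C.1).
- Form by age: SIQ at 15 and over, SIQ-JR below 15 (X.C.1).
- Range: 15 items scored 0 to 6 (V.C.4), so the maximum is 15 × 6 = 90.
- VII.C.e trigger: strictly above a cutoff c, not stated.

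**Step 1. SIQ, age 15 and over.** Scores that are both ≥ 30 and < 37 are 30, 31, 32, 33, 34, 35 and 36, which is 36 − 30 + 1 = 7 integer scores.

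**Step 2. SIQ-JR, under 15.** No score is both ≥ 23 and < 16, so this form has no band that is severe but not escalated. The mismatch runs the other way: 16 to 22, or 22 − 16 + 1 = 7 scores, are escalated although below the severe mark. The younger group is escalated before the severe mark and the older group only after it.

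**Step 3. Does VII.C.e resolve the SIQ conflict?** Compare a trigger strictly above c with the X.C.1 start at 37:

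| Cutoff c | Scores in 30–36 triggered by VII.C.e but not by X.C.1 |
|---|---|
| 29 or lower | all seven, 30–36 |
| 30 | six, 31–36 |
| 35 | one, 36 |
| 36 | none; both rules start at 37 |
| above 36 | none in this band |

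The two safety sections contradict each other if c is 35 or lower. If c is 36 or higher they agree on this band, and the disagreement with V.C.4 remains. No value of c removes every inconsistency while V.C.4 stands as written.

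**Step 4. How often the rule is applied.** Table 2 schedules the SIQ or SIQ-JR at all five assessments (CM1 to CM5), and X.C.1 applies the rule at the close of every study visit. The documents give no distribution of scores, so the share of participants in the band cannot be stated.

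**The case against.** The best defence is that the two figures do different jobs. V.C.4 describes an instrument in an analysis section, covers six months of ideation and directs nobody to act. X.C.1 is the only numeric SIQ safety rule and concerns current risk. On this view VII.C.e speaks generally and X.C.1 supplies its number. A severity mark and an action trigger may legitimately differ, but the protocol never says that these do. X.C.1 applies the same SIQ total to current risk, and V.C.1 applies the SIQ to imminent risk. The measure of the last few days is the SIQ-Past Few Days, and the total is the gate to it. A gate set above the protocol's own severe mark needs a stated reason, particularly when the SIQ-JR gate lies below its severe mark.

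The second defence is the safeguards, and these are real. Staff may act on their own judgement whatever the score (VII.C.b). Assistants note worrying responses and must review disclosures with the Local Project Director, and anyone staff are concerned about gets a safety plan (VII.C.e). All youth are referred to care (III.A, V.C.5.F.f). These measures reduce the risk but do not replace a consistent score-based trigger. The consent form and procedures manual may also state a cutoff, but they are not available here.

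Three stronger readings are tempting, and the documents do not support them.

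- *The rule under-triages participants.* That requires 30 to be the correct figure, which the documents do not establish. The error may lie in V.C.4.
- *Staff have no score-based instruction for 30–36.* They do: X.C.1 covers every SIQ score below 37.
- *The plan expects many scores in this band.* III.B says "an average baseline score of 45 could be expected on the SIQ", and 45 × 0.75 = 33.75 lies inside it. But III.B uses the 25% fall as a benchmark for clinical significance and powers the trial on a smaller effect, Cohen's F = 0.2. So 33.75 is not a planned mean, and no share of participants in the band can be derived.

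**Conclusion.** The contradiction stands on the protocol's own text. For ages 15 and over, seven scores (30 to 36) are labelled severe and in need of intervention in V.C.4, and placed in the lowest risk category in X.C.1. VII.C.e does not resolve this because it gives no number, and it conflicts with X.C.1 if the developers' cutoff is 35 or lower. The SIQ-JR figures differ in the cautious direction, and the reversal is unexplained.

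The conclusion assumes that V.C.4 and X.C.1 refer to the same SIQ total, that the mark in V.C.4 means 30 or greater, as in III.B, and that VII.C.e means strictly above its cutoff. Under-triage of this band is possible but not proven, and the safeguards cover part of it. This is a matter of participant safety and protocol consistency, not of the validity of the treatment comparisons.

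**What to change.** 1. Check the cutoffs for both forms against the instrument manual (reference 21).
2. State one numeric action threshold per form, in the same words, in V.C.4, VII.C.e and X.C.1, and in the consent form and procedures manual if they give one. If 37 is meant as an action trigger distinct from a severity mark of 30, say so and give the reason. Do the same for 16 and 23 on the SIQ-JR.
3. Until this is settled, give the SIQ-Past Few Days at the lower figure for each form: SIQ 30 or above, SIQ-JR 16 or above. The second is already the X.C.1 rule, so in practice only participants aged 15 and over who score 30 to 36 are affected.

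The cost is a wording change, some extra brief screens and calls to the Local Project Director, and probably an IRB amendment. The number of extra screens cannot be estimated from the documents. If 37 proves correct, the interim step will have cost only those screens and calls.

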After 30 days from CM3, all youth will be visited by Research Program Assistants and complete a fourth assessment (CM4). The 30-day time frame between CM3 and CM4 will allow ample time to complete the ER intervention with participants and assess any changes in resilience across study groups. To track long-term outcomes, all youth will complete a final assessment 3 month later (CM5: 6 months post-enrollment). All youth will be followed to the end of the study period (up to 4.75 years from the first participant’s enrollment) for any subsequent suicide events using the Apache surveillance system. If necessary, assessments may be conducted over the phone for participants who start in the study but are located elsewhere during an assessment timepoint.

As part of the economic evaluation supplement, our staff will be asked to fill out time logs listing how they spent time the preceding day. This will not affect the study participants in any way.

Aim 3: STUDY PROCEDURE

If stakeholders provide informed consent, they will be interviewed by Drs. [name] or [name] using a semi-structured guide to gather their views on the Southwest Hub’s key intervention components (Surveillance/Case Management, New Hope and Elders’ Resilience Interventions). They will also be asked to participate in a 2x annually administered online survey to better understand how capacity for sustainability changes over time. If they consent to the online survey, the Program Sustainability Assessment Tool (PSAT) will be administered via email to participants every six months.

2. Describe the number and type of study visits and/or contacts between the study team and the participant, how long they will last, and where/how they will take place.

Aim 1: Five study visits will take place over the course of 6 months. All study visits will take place in the participants' home or a private location.

CM1: Recruitment, consent, randomization, baseline assessment: 2 hours

Intervention Group: NH: 2-4 hours

CM2: Assessment: 1 hour

CM3: Assessment and randomization: 1 hour

Intervention Group: EC: 2-4 hours

CM4: Assessment: 1 hour

CM5: Assessment: 1 hour

Opioid Data Collection Sub-Study (for a subset): Additional 60-90 minutes interview

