COVID-19 Questions: Historically, Native American populations have been extremely vulnerable to severe respiratory illnesses. They also experience large disparities in underlying conditions that increase their risk of COVID-19 related morbidity and mortality. The mitigation strategies for COVID-19 also may increase risk of suicide given the association between social isolation and suicidal behavior. We developed 47 multiple choice questions, with community input, to assess COVID-19 exposure, risk, resilience factors, and historical trauma. These questions take approximately 10-15 minutes to complete and will be asked at each study timepoint.

Safety assessment only: The Opioid Risk Tool (ORT) is a brief, self-report screening tool designed by the NIDA.

Patients categorized as high-risk are at increased likelihood of future abusive drug-related behavior. This will be explained to parents and youth in the consent forms. ORT can be administered and scored in less than 1 minute and has been validated in both male and female patients. The Risk Tool is embedded in the REDCap survey and participants are shown the tool if they endorse any opioid items. Although the ORT is in the assessment, it will not be used for research purposes; it will only be used to ensure the safety of participants.

Aim 3:

Acceptability and feasibility will be measured using 13-item and 20-item scales, respectively. Both scales were developed by researchers at Johns Hopkins to measure implementation of mental health programs in low resource settings. Items included in these scales are based on leading implementation science frameworks (Consolidated Framework for Implementation; Reach, Effectiveness, Adoption, Implementation, and Maintenance; and a conceptual model of evidence based implementation in public services sectors)[36-38], as well as knowledge gathered from health systems, dissemination and implementation science experts. The scales have demonstrated good psychometric properties across a range of stakeholder groups in low income settings internationally (alpha=0.79 and alpha=0.77).[39, 40] Each scale is scored on a 4-point ordinal scale ranging from 0 “not at all” to 3 “a lot,” with an additional category for “don’t know/not applicable.”

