A. Describe the risks, discomforts, and inconveniences associated with the study and its procedures, including physical, psychological, emotional, social, legal, or economic risks, and the risk of a breach of confidentiality. These risks should be described in the consent documents.

Aim 1: All participants will be informed about any *potential risks*. The main potential risks to youth enrolled in the programs are: a) the possibility of discomfort in completing the assessments; b) worsening of symptoms; c) breach of confidentiality including sensitive data regarding opioid use; and d) the need to report to tribal/state authorities for dangerousness to self or others or if the participant is a victim of abuse. If youth or adults are identified as using or abusing opioids, the above risks apply for the qualitative interviews to which they will separately consent.

The main additional risk would be the requirement to undergo an additional opioid abuse assessment (described above) to continue in the parent study, which may include additional discomfort. In the case of minors, another risk is the possibility of having to disclose their opioid abuse to their parents. Specifically, when a youth participant is identified at high risk from their own opioid use, research staff would share with the youth's parent(s): the opioid use (of which the parent may or may not be aware); the determination of high risk; the referral information; and the importance of the parent(s) following through on the referral for their youth. Per the Opioid Risk Tool scoring guidelines, a score of 3 or lower indicates low risk for future opioid abuse, a score of 4 to 7 indicates moderate risk for opioid abuse, and a score of 8 or higher indicates a high risk for opioid abuse. We would consider a score of 8 or higher to necessitate parent notification. In the moderate risk level, we will encourage and support youth to talk with their parents about their opioid use, but would not require disclosure.

Other risks not known now may occur during study participation.

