An imminent risk procedure was developed by WMAT-CAIH as part of previous studies to ensure triage and access to emergency care for youth who are at immediate risk for suicide. This procedure was approved by Tribal, Hopkins and IHS IRBs, and will be employed by CMHWs for this project (see *Protection of Human Subjects*). At the close of each visit, youth will complete the Suicide Ideation Questionnaire (SIQ/SIQ-JR) (see *Appendix*). CMHWs immediately score SIQ at the time of visit, and depending on score will respond in a graduated fashion. The staff member also has the training and discretion to recognize high risk individuals and will act accordingly, even if SIQ does not indicate risk.

c. Identified to be Using or Abusing Opioids:

If current opioid use is identified through our supplement, a two-fold strategy will be used. First, once opioid related items are approved to be added to the surveillance system, substance specific referrals and case management will be covered by the surveillance system. Second, an additional opioid abuse assessment will be conducted to ensure the safety of participants in the SMART trial who endorse current or recent use. This assessment would be conducted *at the study visit*. This assessment will allow the study team to determine if

the participant can continue in the trial, in addition to get them into the most appropriate treatment. All participants who endorse opioid use will receive referrals.

d. Risk of a Breach in Confidentiality

There are two methods by which participants' confidentiality can be breached, including inadequate safeguards of the collected data and a direct breach of confidentiality by study personnel. The consent form will describe in detail the methods used to protect participants' confidentiality and those individuals and entities (i.e., Johns Hopkins IRB, NIH) that have access to the data. As mentioned above, we will obtain a Certificate of Confidentiality for this study. We will explain to the participants that we will have obtained this Certificate of Confidentiality as added protection for their privacy.

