of doing mental health research with high-risk participants. Relationships with referral agencies include Apache Behavioral Health Services, Rainbow Treatment Center and Indian Health Services Social Services Department. Research staff will encourage both adult and youth participants to disclose their use to parents with research staff support in order to engage a familial support system for youth related to opioids. Our staff will remind the participant of the study protocol which would have been explained to them during consent. A participant may refuse the opioid abuse assessment at the time of the study visit. In this case, they would be required to have the opioid abuse assessment conducted before the next intervention or study visit to continue in the parent grant and supplement.

Note: Parent/guardian will be notified during the consent process that their child's responses to the items on the study instruments will not be shared with them. However, if immediate triage of study participants is required due to the identified worsening of symptoms or using or abusing opioids, the Research Program staff member will notify the parent/guardians of the <18 year old participants at the same time that the appropriate tribal authorities are notified. For study participants aged 18-19, it is not required that the Research Program staff notify the parent or guardian, but Research Program staff will attempt to do so with the study participant's verbal permission.

Aim 3: We expect minimal risk, however, [name], a clinical psychologist, and be available if unexpected issues arise.

2. If a Data Safety Monitoring Board (DSMB), or equivalent will be established, describe the following:

This section only applies to Aim 1. Aim 3 will not have a DSMB.

- a. The DSMB membership, affiliation and expertise.

The Data and Safety Monitoring Board (DSMB) will be comprised of a group of independent experts that advises the Southwest Hub and will include at a minimum, one suicide expert, one tribal nations expert, and one biostatistician.

- b. The charge or charter to the DSMB.

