In cases where participants score in the high-risk category on the Opioid Risk Tool, the local research staff will consult with the two Co-PIs to determine if the participant can continue in the parent study. The parent study is an effectiveness trial, where participants can receive other services as necessary. The main factor for deciding whether they can continue in the trial is whether participating in our study is interfering with them participating in needed opioid treatment (i.e., participation in our trial may be a barrier to the time commitment needed for substance use treatment) or vice versa—i.e., participation substance abuse treatment may be a barrier to the time commitment needed to participate in our trial.

D. Reporting Unanticipated Problems/Adverse Events (AE's) to the IRB (all studies must complete this section):

Aim 1 & 3: Describe your plan for reporting to the IRB and (if applicable) to the sponsor. Include your plan for government-mandated reporting of abuse or illegal activity.

The Research Program staff will immediately alert the Local Project Director and PIs in the event of an adverse event or unanticipated problem. The PIs, Drs. [name] and [name], and the Clinical Research Supervisor, [name], will report serious adverse events to the JHSPH IRB if it is unanticipated, poses risk of harm to participants or others, and is related to the study. If there is any suspected harm to self, others, or abuse reported during an interview (including those related to opioid use), the Research Program staff will immediately report this information to the PIs. The PIs and the Local Project Director will report this to appropriate Tribal or Law Enforcement Authorities. With experience from previous studies with the White Mountain Apache community, the study team is knowledgeable of how to report this type of event without revealing study participation.

NOTE: The IRB does not require submission for all AEs, only those that are **unanticipated, pose risk of harm to participants or others, and are related to the study.**

E. Other IRBs/Ethics Review Boards:

If other IRBs will review the research, provide the name and contact information for each IRB/ethics review board and its Federal Wide Assurance, if it has one (available on OHRP's website at <http://www.hhs.gov/ohrp/assurances>).

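### Continued refusal of the safety-only Opioid Risk Tool ends SIQ collection: a modest, avoidable risk of selective loss in the primary outcome

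*Combined protocol and SAP*

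**What the plan says.** - **The condition.** Section X.C.1 (Safety Monitoring, opioid sub-study paragraph) allows refusal of the opioid abuse assessment at the visit itself. The participant is then "required to have the opioid abuse assessment conducted before the next intervention or study visit to continue in the parent grant and supplement". Section VII.A lists the same thing among the risks, as the "requirement to undergo an additional opioid abuse assessment (described above) to continue in the parent study". Section X.C.1 names the instrument as the Opioid Risk Tool.
- **The status of the tool.** It appears only for those who endorse an opioid item. Section V.C.4 says "it will not be used for research purposes; it will only be used to ensure the safety of participants".
- **High scores.** These lead to a review and not to automatic exit: "the local research staff will consult with the two Co-PIs to determine if the participant can continue in the parent study" (section X.C, under interim analysis and stopping rules). The main question there is "whether participating in our study is interfering with them participating in needed opioid treatment".
- **Referral.** Section VII.C.c: "All participants who endorse opioid use will receive referrals".
- **Follow-up outside the visits.** Section V.C.1 follows all youth to study end, but "for any subsequent suicide events using the Apache surveillance system". Phone assessment is offered to participants who are located elsewhere.
- **Outcome and schedule.** The SIQ is the primary outcome and is scheduled at CM1 to CM5 (section V.C.4 and Table 2). Re-randomisation takes place at CM3.

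**The concern.** The condition in section X.C.1 covers study visits as well as intervention sessions. A participant who goes on declining a tool that supplies no research data therefore stops supplying the research data the trial exists to collect, and does so after randomisation.

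The group affected is not a random one. It consists of people who report opioid use, which section VIII.B describes as a possible risk factor for later suicidal behaviour. Their missing SIQ scores may differ systematically from those observed. The analysis plan's only answer to missing data is a general statement that mixed models cope well with it. That gives little comfort for someone who leaves after CM1 with a baseline score alone, from whom the model learns nothing about change.

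The rule is also stricter on decliners than on confirmed high scorers. The latter get an individual review by the Co-PIs, and no section offers one to the former.

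**Working it through.** **1. Does anything in the plan keep SIQ collection going after this exit?** I compared the sections that might.

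- V.C.1 has all youth completing the later assessments. This is the general schedule and makes no exception to the X.C.1 condition.
- V.C.1 and V.C.3 on follow-up to study end cover suicide events from surveillance, not SIQ scores.
- The phone option is for people who are elsewhere, not for people who decline the tool.
- V.C.1 describes case management visits that include "use of the Suicide Ideation Questionnaire (SIQ) to assess imminent risk", and V.C.5.F says such care may continue after the study. No section says those scores would count as trial outcomes.
- V.C.5.F.d (removal), X.C.1 (discontinuation for opioid abuse) and X.C (high-score review) provide no outcome collection after exit.

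Nothing fills the gap.

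**2. Loss per participant.** This assumes the battery at the visit of refusal is completed and the refusal is never reversed.

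| Refusal at | SIQ scores kept | SIQ scores lost | Six-month score | Reaches CM3 re-randomisation |
|---|---|---|---|---|
| CM1 | 1 | 4 | lost | no |
| CM2 | 2 | 3 | lost | no |
| CM3 | 3 | 2 | lost | yes |
| CM4 | 4 | 1 | lost | yes |
| CM5 | 5 | 0 | kept | yes |

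**3. How many participants?** The documents give neither an endorsement rate nor a refusal rate. The one anchor is the sub-study's target of 30 interviews with endorsers (section I), which presumes at least 30 of them: 30/304 = 9.9%. I assume 9.9% to 30% endorse use and 5% to 20% of those keep declining.

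- Low: 30 × 0.05 = 1.5 participants, and 1.5/304 = 0.5%.
- High: 0.30 × 304 = 91.2 endorsers; 91.2 × 0.20 = 18.2 participants, and 18.2/304 = 6.0%.

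**4. SIQ scores lost.** Planned scores: 304 × 5 = 1,520.

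- Ceiling, with every refusal at CM1: 1.5 × 4 = 6 (0.4%) to 18.24 × 4 = 73 (4.8%).
- Refusals spread evenly over the five visits: mean loss (4+3+2+1+0)/5 = 2 scores, so 1.5 × 2 = 3 (0.2%) to 18.24 × 2 = 36 (2.4%).

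**5. Effect on the six-month contrast.** With equal loss in each arm, shift = share leaving × (effect in stayers − effect in leavers). As a deliberately large difference I take the whole clinically significant change in section III.B: 0.25 × 45 = 11.25 points.

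- Ceiling, all leavers losing the six-month score: 0.0049 × 11.25 = 0.06 to 0.06 × 11.25 = 0.68 points.
- Even spread, with four-fifths of refusals losing that score: 0.0049 × 0.8 × 11.25 = 0.04 to 0.06 × 0.8 × 11.25 = 0.54 points.
- Even spread and half the difference: 0.02 to 0.27 points.

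**6. Against the attrition allowance.** Section III.B allows 30%, which is 0.30 × 304 = 91 participants. The 1.5 to 18.2 leavers would use 2% to 20% of that. Counted instead as the surplus of 304 over the 4 × 58 = 232 that the calculation needs, the room is 72 participants, and the leavers still fit unless other losses are heavy.

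**The case against.** The gate is a deliberate and disclosed safety choice in suicidal young people who use opioids. Section VII.C.c says the assessment helps decide whether a participant can continue. Section VII.A declares it as a risk, and staff are to remind participants of what was explained at consent. The trigger is also narrow. A participant must endorse use although any question may be skipped, then decline a tool that takes under a minute, and keep declining until the next contact. Nothing bars someone from resuming once the tool is done, and section V.C.5.F.d does not list refusal among its removal reasons. The same absence of later SIQ collection applies to people who move or are discontinued for other reasons. The sizes above rest on assumed rates.

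Most of this stands. It sets the priority, and it is why the gate on treatment delivery should remain. It does not explain why consented outcome visits must also stop. Removing a persistent decliner does not produce the missing score, and it ends visits that close with an SIQ risk screen.

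Three stronger readings are tempting, and the documents support none of them:

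- **Arms lose participants unequally.** A reader might infer this because the deadline is the next intervention or study visit, which can come sooner for someone allocated to New Hope or Elders' Resilience. No refusal figures by arm exist, and no difference is shown.
- **The trial becomes underpowered.** The plausible numbers probably fall within the attrition allowance. The allowance covers lost numbers, though, and not selective loss.
- **A high score, or one refusal, means automatic permanent exit.** High scores go to the Co-PIs, and a refusal that is reversed in time costs nothing.

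**Conclusion.** The point holds as a modest risk of selective loss in the primary outcome. Sections X.C.1 and VII.A, followed as written, stop SIQ collection for a participant who keeps declining a tool that is not a research measure, and no other section restores it. The per-person loss of 4, 3, 2 or 1 of 5 scores follows directly from the visit schedule.

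Everything beyond that is assumption. About 0.5% to 6.0% of participants might leave, and the six-month contrast might move by 0.06 to 0.68 SIQ points when all refusals fall at CM1 and leavers differ by a full 11.25 points. Both of those conditions are ceilings. That the loss is informative is plausible from section VIII.B but is not demonstrated. The consent forms are not in the text, and the conclusion does not depend on them. Priority: low to moderate.

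**What to change.** Amend sections VII.A and X.C.1 so that an outstanding or declined Opioid Risk Tool may hold back delivery of New Hope or Elders' Resilience, but does not end the CM2 to CM5 outcome assessments (SIQ with its risk screen, and the Resilience Scales) for participants who still consent to them. In addition:

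- keep referral for everyone who endorses opioid use;
- re-randomise at CM3 all who attend, as section V.C.1 already states, and analyse them as randomised whether or not the intervention was delivered;
- log refusals by arm and visit, so that the loss can be reported alongside the opioid responses already collected at each visit.

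The cost is protocol and consent wording. The real downside is somewhat less leverage to obtain the score used for parent notification (section VII.A) and Co-PI review (section X.C), since some participants may complete the tool only because continuing depends on it. Keeping the gate on intervention delivery preserves part of that leverage.
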